# • Hyperthyroidism or Hypothyroidism:

Thyroid disorders can occur at any time during treatment. Monitor subjects for changes in thyroid function (at the start of treatment, periodically during treatment, and as indicated based on clinical evaluation) and for clinical signs and symptoms of thyroid disorders.

- o Grade 2 hyperthyroidism events (and Grade 2-4 hypothyroidism):
  - In hyperthyroidism, non-selective beta-blockers (e.g. propranolol) are suggested as initial therapy.
  - In hypothyroidism, thyroid hormone replacement therapy, with levothyroxine or liothyroinine, is indicated per standard of care.
- Grade 3-4 hyperthyroidism
  - Treat with an initial dose of IV corticosteroid followed by oral corticosteroids. When symptoms improve to Grade 1 or less, steroid taper should be started and continued over no less than 4 weeks. Replacement of appropriate hormones may be required as the steroid dose is tapered.

## Hepatic:

- For **Grade 2-4** events, monitor with liver function tests (weekly or more frequently until returned to baseline values or is stable.
  - Treat with IV or oral corticosteroids
- When symptoms improve to Grade 1 or less, a steroid taper should be started and continued over no less than 4 weeks.

## • Renal Failure or Nephritis:

- For **Grade 2-4** events, treat with corticosteroids (prednisone 1-2 mg/kg or equivalent) followed by taper.
- When symptoms improve to Grade 1 or less, steroid taper should be started and continued over no less than 4 weeks.
- Monitor changes in renal function
- **Management of Infusion Reactions**: Signs and symptoms usually develop during or shortly after drug infusion and generally resolve completely within 24 hours of completion of infusion. Table 5 below shows treatment guidelines for subjects who experience an infusion reaction associated with administration of pembrolizumab (MK-3475).

Table 4. Infusion Reaction Tr	reatment Guidelines
-------------------------------	---------------------

NCI CTCAE Grade	Treatment	Premedication at subsequent dosing
Grade 1 Mild reaction; infusion interruption not indicated; intervention not indicated	Increase monitoring of vital signs as           ction; infusion interruption         medically indicated until the subject is           cated; intervention not         deemed medically stable in the opinion of the	
Grade 2 Requires infusion interruption but responds promptly to symptomatic treatment (e.g., antihistamines, NSAIDS, narcotics, IV fluids); prophylactic medications indicated for < =24 hrs	Stop Infusion and monitor symptoms. Additional appropriate medical therapy may include but is not limited to: IV fluids Antihistamines NSAIDS Acetaminophen Narcotics Increase monitoring of vital signs as medically indicated until the subject is deemed medically stable in the opinion of the investigator. If symptoms resolve within one hour of stopping drug infusion, the infusion may be restarted at 50% of the original infusion rate (e.g., from 100 mL/hr to 50 mL/hr). Otherwise dosing will be held until symptoms resolve and the subject should be premedicated for the next scheduled dose. Subjects who develop Grade 2 toxicity despite adequate premedication should be permanently discontinued from further trial treatment administration.	Subject may be premedicated 1.5h (± 30 minutes) prior to infusion of pembrolizumab (MK- 3475) with: Diphenhydramine 50 mg po (or equivalent dose of antihistamine). Acetaminophen 500-1000 mg po (or equivalent dose of antipyretic).
Grades 3 or 4 Grade 3: Prolonged (i.e., not rapidly responsive to symptomatic medication and/or brief interruption of infusion); recurrence of symptoms following initial improvement; hospitalization indicated for other clinical sequelae (e.g., renal impairment, pulmonary infiltrates)	Stop Infusion. Additional appropriate medical therapy may include but is not limited to: IV fluids Antihistamines NSAIDS Acetaminophen Narcotics Oxygen Pressors Corticosteroids Epinephrine	No subsequent dosing
Grade 4: Life-threatening; pressor or ventilatory support indicated	Increase monitoring of vital signs as medically indicated until the subject is deemed medically stable in the opinion of the investigator. Hospitalization may be indicated. Subject is permanently discontinued from further trial treatment administration. should be available in the room and a physician	

# 5.6 Diet/Activity/Other Considerations

# 5.6.1 Diet

Subjects should maintain a normal diet unless modifications are required to manage an AE such as diarrhea, nausea or vomiting.

# 5.6.2 Contraception

Pembrolizumab may have adverse effects on a fetus in utero. Furthermore, it is not known if pembrolizumab has transient adverse effects on the composition of sperm. Non-pregnant, nonbreast-feeding women may be enrolled if they are willing to use 2 methods of birth control or are considered highly unlikely to conceive. Highly unlikely to conceive is defined as 1) sterilized surgically or as a result of radiation treatments, or 2) postmenopausal (a woman who is  $\geq$ 45 years of age and has not had menses for greater than 1 year will be considered postmenopausal), or 3) not heterosexually active for the duration of the study. The two birth control methods can be either two barrier methods or a barrier method plus a hormonal method to prevent pregnancy. Subjects should start using birth control from study Visit 1 throughout the study period up to 120 days after the last dose of study therapy, or until they are no longer of childbearing potential.

The following are considered adequate barrier methods of contraception: diaphragm, condom (by the partner), copper intrauterine device, sponge, or spermicide. Appropriate hormonal contraceptives will include any registered and marketed contraceptive agent that contains an estrogen and/or a progestational agent (including oral, subcutaneous, intrauterine, or intramuscular agents).

Subjects should be informed that taking the study medication may involve unknown risks to the fetus (unborn baby) if pregnancy were to occur during the study. In order to participate in the study they must adhere to the contraception requirement (described above) for the duration of the study and during the follow-up period. If there is any question that a subject will not reliably comply with the requirements for contraception, that subject should not be entered into the study.

# 5.6.3 Use in Pregnancy

If a subject becomes pregnant while on treatment with pembrolizumab, the subject will immediately be removed from the study. The site will contact the subject at least monthly and document the subject's status until the pregnancy has been completed or terminated. The outcome of the pregnancy will be reported to the Sponsor-Investigator. If the outcome is a serious adverse experience (e.g., death, abortion, congenital anomaly, or other disabling or life-threatening complication to the mother or newborn), this should be reported within 24 hours to the Sponsor-Investigator.

The study investigator will make every effort to obtain permission to follow the outcome of the pregnancy and report the condition of the fetus or newborn to the Sponsor-Investigator.

# 5.6.4 Use in Nursing Women

It is unknown whether pembrolizumab is excreted in human milk. Since many drugs are excreted in human milk, and because of the potential for serious adverse reactions in the nursing infant, subjects who are breast-feeding are not eligible for enrollment.

# 5.7 Subject Participation and Withdrawal/Discontinuation Criteria

A subject is considered On-Study from the time eligibility is confirmed through the follow-up interval. Subjects may withdraw consent at any time for any reason or be dropped from the trial at the discretion of the investigator should any untoward effect occur. In addition, a subject may be withdrawn by the investigator or the Sponsor-Investigator if enrollment into the trial is inappropriate,

Protocol/Amendment No.: UVA-LACC-PD201, Version 4.0, 06 March 2018

the trial plan is violated, or for administrative and/or other safety reasons. Specific details regarding discontinuation or withdrawal are provided in the sections below.

## 5.7.1 Duration of Treatment

Subjects will continue to receive study treatment (defined as chemoradiation and pembrolizumab) until:

- Subject has completed all study treatments
- Disease progression
- Unacceptable adverse event(s)
- Subject withdraws consent for further treatment
- · Female subject has a confirmed positive serum pregnancy test
- Subject receives a non-study treatment (not protocol-specified) for their cancer
- Subject non-compliance
- General or specific changes in the subject's condition render the subject unacceptable for further treatment in the judgment of the investigator

If any of the above events occurs, the subject will be considered off treatment and in follow-up. Subjects will be followed for 5 years for PFS and OS, or until the trial is terminated per Section 5.7.4.

## 5.7.2 Discontinuation/Withdrawal from Study

Subjects may withdraw or be discontinued from the study at any time for any of the following reasons:

- Subject decides to withdraw from the study
- Subject is unable or unwilling to complete the follow-up procedures
- The subject is lost to follow-up
- Death

The primary reason for discontinuation or withdrawal should be entered into OnCore. All subjects that discontinue or withdraw from the study will continue to receive standard of care treatment. Subjects who have withdrawn consent for the study will not be followed for any reason.

A subject's participation is considered completed when the subject has completed the 5 year followup interval.

## 5.7.3 Subject Status Definitions

Enrolled: All subjects who sign an informed consent will be considered enrolled on the study. All subjects consented on the study must be entered into OnCore.

Screen Failure: A subject who is withdrawn or discontinues from the study prior to receiving any treatment is considered a post enrollment screen failure. Post enrollment screen failures are not considered a study accrual and will be replaced. Note: The UVa IRB-HSR defines any individual that has signed an informed consent as an enrollment in this study and so screen failures should be reported to the IRB with enrollment numbers.

Protocol/Amendment No.: UVA-LACC-PD201, Version 4.0, 06 March 2018

On-Study: A subject is considered on-study on the date when the study team has confirmed the subject has met all of the inclusion and none of the exclusion criteria, and the treating physician/surgeon or study PI has signed off on the confirmation.

Randomized: A subject that has been randomized to an arm is considered a randomized subject.

On-Treatment: A subject is considered on-treatment on the date that CRT is initiated

Off-Treatment: A subject is considered off-treatment on the date that they have met any of the criteria listed in Section 5.7.1

On Follow-up: A subject is considered on follow-up on the date that they have met any of the criteria listed in Section 5.7.1.

Off-Study: A subject is considered off-study if they are removed from the study for any of the reasons listed in Section 5.7.2, or if they have completed the follow-up interval.

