#### Table 1 Adequate Organ Function Laboratory Values

System	Laboratory Value
Hematological	
Absolute neutrophil count (ANC)	≥1,500 /mcL
Platelets	≥100,000 / mcL
Renal	
Serum creatinine OR	≤1.5 X upper limit of normal (ULN) OR
Measured or calculated a creatinine	
clearance	≥60 mL/min for subject with creatinine levels > 1.5 X
(GFR can also be used in place of	institutional ULN
creatinine or CrCl)	
Hepatic	
Serum total bilirubin	≤ 1.5 X ULN OR
	Direct bilirubin ≤ ULN for subjects with total bilirubin levels
	> 1.5 ULN
	≤ 2.5 X ULN OR
AST (SGOT) and ALT (SGPT)	≤ 5 X ULN for subjects with liver metastases
Albumin	> 2.5 mg/dL
Coagulation	
International Normalized Ratio (INR) or	≤1.5 X ULN unless subject is receiving anticoagulant
Prothrombin Time (PT)	therapy as long as PT or PTT is within therapeutic range of
	intended use of anticoagulants
	-

Activated Partial Infomboplastin Time	≤1.5 X ULN unless subject is receiving anticoagulant therapy as long as PT or PTT is within therapeutic range of intended use of anticoagulants
a Creatinine clearance should be calculat	ted per institutional standard.

- 6. Female subject of childbearing potential should have a negative urine or serum pregnancy within 72 hours prior to receiving the first dose of study medication. If the urine test is positive or cannot be confirmed as negative, a serum pregnancy test will be required.
- 7. Subjects of childbearing potential should be willing to use 2 methods of birth control or be surgically sterile, or abstain from heterosexual activity for the course of the study through 120 days after the last dose of study medication, or until they are no longer of child bearing potential.

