# 5.7.5 Trial Blinding/Masking

This is an open-label trial; therefore, the Sponsor-Investigator, investigator and subject will know the treatment administered.

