## 7.2 Sample size and accrual

Results in Jordanova ES, et al 2008, report estimates of CD8+/Treg for normal cervix and cervical cancers tissue for cervical cancer patients who underwent radical hysterectomy with lymphadenectomy.[4] These data provide the assumed "natural baseline" of cancer patients' in this study with CD8+/Tregs being lower in cancer tissue, and results in a Cohen's *d*av effect size (ES) of 0.45. Estimated sample size is based upon being able to detect a similar effect size between CD8+/Tregs at baseline and end of CRT, and baseline to the 12 weeks post CRT assessment without correction for multiple comparisons. Data from Nilges, K et al, 2003, indicates a mean (standard deviation) of 23.32 (15.39) in CD8+/Tregs measured in the tumor infiltrating lymphocytes (TIL) from patients with cervical cancer. Given these data, 44 eligible patients are required (per arm) to assess change in pre/post CD8+/Tregs with an ES of 0.45 with type I and II errors of 10%. Each within arm comparison supports the following hypothesis. Cisplatin can kill T cells, therefore the CRT may eliminate both CD8+ HPV CTL and Tregs, and the ensuing or concurrent pembrolizumab treatment may increase the CD8+/Treg ratio (test that pembrolizumab will increase CD8+/Tregs to an ES of 0.45).

Adjusting for an overall 10% ineligibility/drop-out rate, maximum accrual to the study is estimated at 98 patients. Accrual is estimated at 4 patients a month, thus accrual to the study should be completed by 2.0 years with primary analysis at 3 years.

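### Section 5.7.3 draws the screen-failure line at first treatment, so a patient who leaves after open-label randomisation is replaced and not recorded as a loss from her arm

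*Combined protocol and SAP*

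**What the plan says.** **Status rules (Section 5.7.3).** The definition reads: "A subject who is withdrawn or discontinues from the study prior to receiving any treatment is considered a post enrollment screen failure". The consequence follows: "Post enrollment screen failures are not considered a study accrual and will be replaced". Randomised status is defined separately: "A subject that has been randomized to an arm is considered a randomized subject". No accrual, follow-up or analysis rule is attached to it. The section also notes that "screen failures should be reported to the IRB with enrollment numbers", and it requires every consented subject to be entered in OnCore.

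**Blinding (Section 5.7.5).** "This is an open-label trial; therefore, the Sponsor-Investigator, investigator and subject will know the treatment administered".

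**Order of events.** Section 2.1 randomises eligible subjects. Sections 6.3.1.2 and 6.3.2 have eligibility confirmed at the site and reviewed by the study manager, who also performs the randomisation. No limit is set on the time from randomisation to treatment. In Section 5.1.2 the screening laboratory tests are timed to within 14 days of treatment initiation, and the pregnancy test must be negative "within 72 hours prior to receiving the first dose of study medication". Both are anchored to treatment, not to randomisation.

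**Analysis sets.** Section 7.0 evaluates participants who received any protocol treatment for safety and the primary immunologic endpoint. Section 7.1.2 requires follow-up samples. Section 7.1.3 requires a 12-week PET/CT for metabolic response, and follow-up information on disease status for distant recurrence, PFS and OS. No all-randomised set is defined.

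**Sample size (Section 7.2).** 44 eligible patients per arm, then: "Adjusting for an overall 10% ineligibility/drop-out rate, maximum accrual to the study is estimated at 98 patients".

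**The concern.** Randomisation protects the comparison of arms only if patients stay attached to the arm they drew. Here the line between never in the trial and lost from an arm is placed at first treatment, after the arm is known to patient and investigator. A patient who changes her mind on learning her arm, or who is withdrawn before Day 1, becomes a screen failure and another patient takes her place.

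Such exits need not be balanced. Section 6.1 starts pembrolizumab on Day 1 in Arm 2 and in Week 9 in Arm 1, so the first days of treatment differ. If the patients who leave differ in prognosis between arms, those remaining are no longer comparable, and a report that lists the leavers as screen failures would not show it.

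At stake are the between-arm differences in pre/post change and the PFS and OS estimates by arm, all planned in Section 7.5.

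**Working it through.** **Step 1. Does the rule reach randomised patients?** The Section 5.7.3 test is whether treatment was received. Being randomised is not an exception, so a randomised, untreated patient who leaves the study meets the definition.

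**Step 2. Can she leave after allocation?** Withdrawal for any reason is open to her at any time (Section 5.7), and the investigator or sponsor-investigator may also withdraw her. A second route depends on timing. All entry criteria can be settled before randomisation only if the pregnancy test, where it applies, precedes randomisation and treatment follows within 72 hours of that test. The plan does not require this. If randomisation is earlier, that criterion is assessed after the arm is known.

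**Step 3. Does another section keep her in an arm?** Sections 7.0 and 7.1.1 require treatment, and 7.1.2 requires samples. Section 7.1.3 does not require treatment for PFS and OS. However, Section 5.7.3 enters follow-up through the treatment-ending criteria of Section 5.7.1, and nothing directs that an untreated randomised patient be followed. She is not assured a place in any arm-level set.

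**Step 4. Reproduce the plan's figures.** Inputs from Section 7.2: effect size d = 0.45, type I and II errors of 10%, 10% ineligibility/drop-out, 4 patients a month.

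- Paired t-test, two-sided 10%: power = P(|T| > t(0.95, n−1)), with T noncentral t on n−1 degrees of freedom and noncentrality d√n. At n = 44 the noncentrality is 0.45 × √44 = 2.985 and power is 90.2%. The smallest n reaching 90% is 44. A one-sided test would need 34, so the plan's figure is two-sided.
- Inflation: 88 / (1 − 0.10) = 97.8, rounded up to 98.

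Both reproduce. The sample-size arithmetic is not at fault.

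**Step 5. What the rule does to the counts.** Let w be the share lost between randomisation and treatment. The documents do not give it, so 2% to 10% is an assumption.

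*Replacement as written:* number randomised = 98 / (1 − w), rounded up. Accrual time assumes 4 randomised patients a month, against 98 / 4 = 24.5 months with no loss.

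| w | Randomised | Outside accrual | Months |
|---|---|---|---|
| 2% | 100 | 2 | 25 |
| 5% | 104 | 6 | 26 |
| 10% | 109 | 11 | 27.25 |

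*No replacement, losses on top of the 10%:* evaluable per arm = 44 × (1 − w), rounded down.

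| w | Evaluable per arm | Within-arm power |
|---|---|---|
| 0% | 44 | 90.2% |
| 2% | 43 | 89.6% |
| 5% | 41 | 88.2% |
| 10% | 39 | 86.8% |

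*No replacement, losses inside the 10%:* 98 × 0.9 = 88.2, so 44 per arm is unchanged.

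These tables size the bookkeeping, not the bias. The bias depends on how losses split by arm and on how the leavers would have fared. The documents give neither.

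**The case against.** **The primary aims are within-arm.** Sections 7.0 and 7.5 say the trial is not built for definitive between-arm comparison. Safety needs exposure and paired immune change needs samples, so untreated patients can inform neither. This stands and limits the point to the between-arm estimates and to PFS and OS.

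**The gap may be short or nil.** Section 5.7.3 grants on-study status only once all entry criteria are confirmed, which suggests randomisation close to treatment. If both fell on one day the opportunity would largely vanish. That is fair, but no section requires it.

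**The incentive to leave is weak.** Both arms receive CRT and three cycles of pembrolizumab, and only the timing differs. This lowers the likely number of arm-driven exits but does not rule them out.

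**Many exits yield no data under any label.** Section 5.7.2 bars follow-up of anyone who has withdrawn consent. The outcome data to be recovered come mainly from patients withdrawn by the investigator or sponsor-investigator. A count by arm is still possible for all of them.

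**The patients are not erased.** They stay in OnCore with a reason for leaving, and in IRB enrolment counts. A reader might infer that they vanish from every record, and that would be wrong. What the plan lacks is a requirement to report them as losses by arm.

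**Conclusion.** The point holds, with modest expected effect. The Section 5.7.3 boundary permits post-allocation exclusion in an open-label trial, and no other section repairs it. The exposed results are the between-arm estimates and arm-level PFS and OS. The size of any bias cannot be computed. The 2% to 10% loss behind the counts above is an assumption, and the route through lapsed eligibility windows also assumes a non-zero interval between randomisation and treatment.

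Three stronger readings are tempting and not supported.

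- *That the plan allows for the same losses twice.* Section 7.2 applies its 10% to accrual, and Section 5.7.3 keeps screen failures out of accrual. Read literally, replacement covers exits before treatment and the 10% covers losses among accrued patients. The plan does not spell this out, but it is not a double allowance.
- *That the rule shifts the complete metabolic response rate by 3 to 7 points.* This comes from adding 2 to 5 non-responders to one arm: 31/44 = 70.5% against 31/46 = 67.4% or 31/49 = 63.3%. Section 7.1.3 admits only patients with a 12-week PET/CT, so untreated patients without that scan stay out whatever their status. Section 5.7.2 says leavers continue standard care, so assuming no responses is extreme. At the 70% rate used in Section 7.5, adding 5 gives (31 + 3.5)/49 = 70.4%, virtually no change.
- *That a lapsed biopsy or MRI window makes a patient ineligible.* These are scheduled procedures in Sections 6.1 and 6.3.4.2.1, not entry criteria in Section 5.1, and the MRI may be omitted at investigator discretion.

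**What to change.** - **Section 5.7.3:** limit screen failure, and therefore replacement, to exits before randomisation. Count every randomised subject in her assigned arm.
- **Sections 6.3.1.2 and 6.3.2:** require all entry criteria to be confirmed before randomisation, and randomise as close to treatment start as is practicable.
- **Reporting:** list randomised-but-untreated subjects by arm, with reasons.
- **Section 7.1.3:** analyse PFS and OS in all randomised eligible subjects by assigned arm, and follow those who have not withdrawn consent. Keep the treated-only set for safety and the existing treatment and sample requirements for the immune endpoints.
- **Section 7.2:** state whether untreated randomised subjects fall inside the 10% allowance or come on top of it.

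The cost is mostly wording, a row in the participant flow diagram, tighter scheduling before Day 1, and follow-up of a few untreated patients. If the 10% covers these losses, 98 and 44 per arm are unchanged. If they come on top and are not replaced, the price is up to about 3.4 points of within-arm power (90.2% to 86.8%) at the assumed 10% loss. The sponsor could instead raise the ceiling and randomise the extra patients in the ordinary sequence, with the earlier ones kept in their arms: 100 to 109 in all for a 2% to 10% loss.
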